## **Intensity**

The intensity of an adverse event must be classified using the following 3-point scale:

- Mild: Awareness of signs or symptoms, but no disruption of usual activity.  
Moderate: Event sufficient to affect usual activity (disturbing).  
Severe: Inability to work or perform usual activities (unacceptable).

## **Causal Relationship to IMP**

The possibility of whether the IMP caused the adverse event must be classified as one of the following:

Reasonable possibility: There is evidence or argument to suggest a causal relationship between the IMP and the adverse event. The adverse event may occur as part of the pharmacological action of the IMP or may be unpredictable in its occurrence.

Examples:

- Adverse events that are uncommon but are known to be strongly associated with IMP exposure.
- Adverse events that are not commonly associated with IMP exposure, but the event occurs in association with other factors strongly suggesting causation, such as a strong temporal association with the IMP or the event recurs on rechallenge with the IMP.

No reasonable possibility: There is no reasonable evidence or argument to suggest a causal relationship between the IMP and the adverse event.

Examples:

- Known consequences of the underlying disease or condition under investigation.
- Adverse events common in the trial population, which are also anticipated to occur with some frequency during the course of the trial, regardless of IMP exposure.

## **Action Taken to IMP**

The action taken to the IMP in response to an adverse event must be classified as one of the following:

- No change (medication schedule maintained or no action taken)
- Discontinued
- Interrupted

- Dose reduced
- Dose increased

### **Other Action Taken**

Adverse events requiring therapy must be treated with recognised standards of medical care to protect the health and well-being of the subject. Appropriate resuscitation equipment and medicines must be available to ensure the best possible treatment of an emergency situation.

If medication is administered to treat the adverse event, this medication should be entered in the Concomitant Medication Log.

### **Date and Time of Outcome**

The date and time the subject recovered or died.

### **Outcome**

The outcome of an adverse event must be classified as one of the following:

- Recovered (fully recovered or the condition has returned to the level observed at initiation of trial treatment)
- Recovered with sequelae (resulted in persistent or significant disability / incapacity)
- Recovering
- Not recovered
- Fatal

## **8.3 Adverse Events of Special Interest and/or Requiring Special Handling**

### **8.3.1 Ovarian Hyperstimulation Syndrome (OHSS)**

#### **Symptoms and Classification**

OHSS is an adverse event of special interest during controlled ovarian stimulation. Investigators will record OHSS symptoms and use these symptoms directly to grade (1, 2, 3, 4 or 5) each OHSS case into Golan's classification system^35 as shown in Table 8-1.

**Table 8-1 Classification of Mild, Moderate and Severe OHSS (Golan’s Classification System)**

Mild OHSS	
Grade 1	Abdominal distension and discomfort
Grade 2	Features of grade 1 plus nausea/vomiting and/or diarrhoea. Ovaries enlarged to 5-12 cm. a)
Moderate OHSS	
Grade 3	Features of mild OHSS plus ultrasonic evidence of ascites. b)
Severe OHSS	
Grade 4	Features of moderate OHSS plus clinical evidence of ascites and/or hydrothorax (or breathing difficulties). Paracentesis due to OHSS symptoms. c)
Grade 5	All of the above plus change in blood volume, increased blood viscosity due to haemoconcentration, coagulation abnormalities, and diminished renal perfusion and function. d) Hospitalisation due to OHSS symptoms.

a) For each ovary, the size will be the average of the greatest diameter and its greatest perpendicular diameter. Ovarian enlargement will be based on the average size of the right and left ovaries. The sizes of both ovaries should be recorded.

b) For subjects with transvaginal evidence of ascites, the size of the fluid pockets in the pelvis (Douglas pouch, vesico-uterine pouch, etc) should be estimated by measuring the greatest diameter and its greatest perpendicular diameter, and multiplying these two numbers (the unit will be cm^2). Peritoneal fluid is the total size of all fluid pockets in the pelvis.

c) In case of paracentesis, the volume of fluid drained should be measured.

d) Heaemoconcentration is defined as haematocrit >45 %. Electrolyte disturbances is defined as hyponatremia (sodium <135 mEq/L) and/or hyperkalemia (potassium >5.0 mEq/L). Coagulation abnormalities are defined as presence of thromboembolic events, abnormal prothrombin time or abnormal activated partial thrombin time. Diminished renal perfusion is defined as creatinine >1.2 mg/dl. Oliguria is defined as urine output less than 500 mL / 24 hours. Anuria is defined as failure to produce urine. If applicable, actual volume of urine output will be recorded.

All cases of OHSS must be reported as adverse events. Those that fall under the category serious adverse events must be reported as such. Note that the classification ‘mild OHSS’, ‘moderate OHSS’ and ‘severe OHSS’ does not refer to the classification of an adverse event’s intensity (also rated mild, moderate, or severe).

Subject narratives will be prepared for all moderate and severe OHSS cases.

Concerning timing, early OHSS will be defined as OHSS with onset ≤9 days after triggering of final follicular maturation and late OHSS will be defined as OHSS with onset >9 days after triggering of final follicular maturation.

In addition to early OHSS and late OHSS overall, emphasis will be placed on OHSS of moderate/severe grade.

### **Preventive Interventions of Early OHSS**

Preventive interventions of early OHSS include the following:

- Cycle cancellation due to excessive ovarian response

- Triggering of final follicular maturation with GnRH agonist

### **Investigations to be Conducted in Subjects where OHSS Symptoms are Observed**

The following investigations must be conducted when OHSS symptoms are first observed and repeated when there are clinically relevant changes in the OHSS presentation:

- Body weight and maximum abdominal circumference (for all OHSS)
- Vital signs (for all OHSS)
- Blood sample for central laboratory analysis of the following (for moderate/severe OHSS):
  - Progesterone and estradiol
  - CBC (red blood cells, red blood cell morphology, white blood cells, white blood cell morphology, haemoglobin, haematocrit, mean corpuscular volume, mean corpuscular haemoglobin, mean corpuscular haemoglobin concentration, platelets)
  - CHEM-20 (alanine transaminase, albumin, alkaline phosphatase, aspartate aminotransferase, bicarbonate, bilirubin direct, bilirubin total, blood urea nitrogen, calcium, chloride, cholesterol total, creatinine, gamma-glutamyl transpeptidase, glucose, lactate dehydrogenase, phosphorus, potassium, sodium, total protein, uric acid)
  - Coagulation parameters (prothrombin time, activated partial thrombin time)

Any treatments of OHSS, e.g. intravenous administration of volume expanders, paracentesis, use of low-molecular-weight heparin and intravenous administration of albumin, must be recorded as concomitant medication.

#### **8.3.2 Local Tolerability**

Injection site reactions after administration of IMP (FE 999049 and GONAL-F) are only to be reported as adverse events if they require active management, i.e. discontinuation of IMP, additional investigations or treatment of the injection site reaction. Local tolerability of IMP constitutes a secondary endpoint and will be evaluated in detail based on the subjects' recordings in the diary.

Local tolerability reactions after administration of NIMP are to be reported as adverse events if they fulfil the definition of an adverse event.

#### **8.3.3 Treatment-induced Anti-FSH Antibodies**

Presence of treatment-induced anti-FSH antibodies is not to be reported as an adverse event. These data will be described as part of the secondary endpoints.

### **8.3.4 Menstrual Bleeding**

Menstrual bleeding is only to be reported as an adverse event in case it is excessive, painful, delayed or in any other way deviating from the subject's normal menstruation. Menstrual bleeding associated with lack of pregnancy will be reported as part of the efficacy evaluation.

### **8.3.5 Ovarian Torsion**

Any case of ovarian torsion will be reported as an adverse event and it will be specified whether it is associated with any signs or symptoms of OHSS.

### **8.3.6 Pregnancy Losses**

The following terminology should be used for reporting of pregnancy losses during the trial:

Biochemical pregnancy:	Positive $\beta$ hCG test but no gestational sac is observed on later transvaginal ultrasound, or menstruation is reported
Spontaneous abortion:	Positive $\beta$ hCG test but all intrauterine gestational sacs are without fetal heart beat as documented by ultrasound, or there are no viable fetuses observed by ultrasound
Vanishing twin:	Spontaneous disappearance of an intrauterine gestational sac with or without heart beat in a pregnancy where one viable fetus remains as documented by ultrasound
Ectopic pregnancy:	Extrauterine gestational sac with or without fetal heart beat as documented by ultrasound or surgery

Concerning timing, a pregnancy loss occurring before ongoing pregnancy (i.e. during 1st trimester) will be defined as an early pregnancy loss, while a pregnancy loss occurring after ongoing pregnancy (i.e. during 2nd or 3rd trimester) during the post-trial follow-up will be defined as a late pregnancy loss.

### **8.3.7 Multiple Pregnancies**

Multi-fetal gestations are not to be reported as adverse events. These data will be described as part of the secondary endpoints.

## 8.4 Serious Adverse Events

### 8.4.1 Serious Adverse Event Definition

#### Serious Adverse Events during the Trial

An event is defined a serious adverse event if it:	Guidance
results in death	Any event resulting in a fatal outcome must be fully documented and reported, including deaths occurring within four weeks after the treatment ends and irrespective of the causal relationship to the IMP. The death of a subject enrolled in a trial is per se not an event, but an outcome.
is life-threatening	The term life-threatening refers to an adverse event in which the subject was at immediate risk of death at the time of the event. It does not refer to an event, which may have caused death if it were more severe.
requires in-patient hospitalisation or prolongation of existing hospitalisation	The term hospitalisation means that the subject was admitted to hospital or that existing hospitalisation was extended as a result of an event. Hospitalisation describes a period of at least 24 hours . Over-night stay for observation, stay at emergency room or treatment on an out-patient basis do not constitute a hospitalisation. However, medical judgement must always be exercised and when in doubt the case should be considered serious (i.e. if case fulfils the criterion for a medically important event). Hospitalisations for administrative or social purposes do not constitute a serious adverse event. Hospital admissions and/or surgical operations planned before trial inclusion are not considered adverse events, if the illness or disease existed before the subject was enrolled in the trial, provided that the condition did not deteriorate during the trial.
results in persistent or significant disability / incapacity	Disability / incapacity means a substantial disruption of a person's ability to conduct normal life functions. In doubt, the decision should be left to medical judgement by the investigator.
is an important medical event	Medical and scientific judgment should be exercised in deciding whether other situations should be considered serious such as important medical events that might not be immediately life-threatening or result in death or hospitalisation but might jeopardise the patient or might require intervention to prevent one of the other outcomes listed in the definition above. Examples of such events are intensive treatment in an emergency room or at home for allergic bronchospasm, blood dyscrasias or convulsions that do not result in hospitalisation, or development of drug dependency or drug abuse.

#### Serious Adverse Events during Post-trial Follow-up

The following untoward medical occurrences reported as part of the pregnancy outcome and neonatal health data collection will be recorded as serious adverse events. Data will be collected at birth and at 4 weeks after birth.

- Death of mother in connection with pregnancy or labour
- Death of neonate

- Stillbirth ( $\geq$  gestational age 24 weeks + 0 days, calculated from the day of transfer + 17 days)
- Neonate admitted to the NICU regardless of duration or NICU for more than 2 hours
- Congenital anomaly / birth defect
- Medically important event

In case of admission to NICU or NICU, the reason for admission must be reported as a serious adverse event, rather than just the act of hospitalisation.

Congenital anomalies will be coded by Ferring using both MedDRA and ICD-10 and classified as minor or majorh in accordance with the EMA guideline.

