## LIST OF ABBREVIATIONS AND DEFINITION OF TERMS

$\alpha$	alfa
AMH	anti-Müllerian hormone
ART	assisted reproductive technologies
ATC	Anatomical Therapeutic Chemical classification system
$\beta$	beta
$\beta$ hCG	beta unit of human chorionic gonadotropin
BMI	body mass index
CBC	complete blood count
CHO	Chinese hamster ovary
CHEM-20	a blood test to measure the level of 20 different proteins, lipids and electrolytes
DHEA	dehydroepiandrosterone
e-CRF	electronic case report form
EMA	European Medicines Agency
FAS	full analysis set
FDA	Food and Drug Administration
FPFV	first patient first visit
FSH	follicle-stimulating hormone
GCP	Good Clinical Practice
GMP	Good Manufacturing Practice
GnRH	gonadotropin-releasing hormone
GPV	Global Pharmacovigilance Department
h	hour(s)
HBsAg	Hepatitis B Surface Antigen
hCG	human chorionic gonadotropin
HCV	Hepatitis C Virus
HIV	Human Immunodeficiency Virus
HLT	high level term
ICD-10	International Statistical Classification of Diseases and Related Health Problems, 10 th revision
ICH	International Conference on Harmonisation
ICMART	International Committee Monitoring Assisted Reproductive Technologies
ICMJE	International Committee of Medical Journal Editors
ICSI	intracytoplasmic sperm injection
IgG	immunoglobulin G
IgM	immunoglobulin M
IMP	investigational medicinal product
IND	investigational new drug
ITT	intention-to-treat
IU	international units
IVF	in vitro fertilisation
L	litre
LH	luteinising hormone
LLOQ	lower limit of quantification
LPFV	last patient first visit

LPLV	last patient last visit
MedDRA	Medical Dictionary for Regulatory Activities
mEq	milliequivalent(s)
mg	milligram
mITT	modified intention-to-treat
MSR	minimum significant ratio
mL	millilitre
NCU	neonatal care unit
ng	nanogram
NIMP	non-investigational medicinal product
NICU	neonatal intensive care unit
OHSS	ovarian hyperstimulation syndrome
PER.C6 ®	host cell line of human fetal retinal origin
PGD	preimplantation genetic diagnosis
PGS	preimplantation genetic screening
pmol	picomol
PP	per-protocol
PT	preferred term
rFSH	recombinant follicle-stimulating hormone
rhCG	recombinant human chorionic gonadotropin
SAE	serious adverse event
SAP	Statistical Analysis Plan
SMQ	Standardised Medical Dictionary for Regulatory Activities (MedDRA) Queries
SUSAR	suspected unexpected serious adverse reaction
TSH	thyroid-stimulating hormone
µg	microgram
ULOQ	upper limit of quantification
US	ultrasound
WHO	World Health Organization

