## **7.4 Assessments Related to Post-trial Information**

### **7.4.1 Pregnancy Follow-up**

For subjects with an ongoing pregnancy, information on the pregnancy period, including any relevant interventions performed and incidence of second or third trimester losses, as well as the pregnancy outcome, e.g. live birth, will be gathered. Further, neonatal health data will be collected at birth and at 4 weeks after birth for all children born. At birth, the data collected will include gender, birth weight and length, way of delivery, position of neonate and Apgar score as well as information on any congenital anomalies and admission to neonatal intensive care unit (NICU) or neonatal care unit (NCU). At 4 weeks after birth, the data collected will include any congenital anomalies, hospitalisations, death of neonate and any other relevant medical conditions. These follow-up data can be obtained from the subject, unless medical judgement is required.

These data will be reported separately.

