#### **14.7 Delivery Data Checklist**

Subjects with a positive ongoing pregnancy will be provided with a checklist for pregnancy follow-up, where the subject will be reminded to report the following information to the investigator:

At delivery:

- Date of delivery
- Way of delivery (vaginal / vacuum extraction / forceps / caesarean section)
- Position of neonate (head / breech / transverse / other – please specify)
- Gender
- Birth weight (kg)
- Birth length (cm)
- Apgar score after 1, 5 and 10 minutes
- Admission to NICU/NCU (reason and duration)
- Neonatal death
- Malformation / congenital anomaly

4 weeks after delivery (any new information since birth):

- Admission to NICU/NCU (reason and duration)
- Neonatal death
- Malformation / congenital anomaly
- Any relevant medical condition

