### **Neonatal Health at Birth and at 4 Weeks after Birth**

Neonatal health at birth and at 4 weeks after birth, including minor/major congenital anomalies, will be summaries for all live-born neonates. Summaries includes delivery details, gestational age, gender, birth weight and birth length. Admission to neonatal intensive care unit and/or neonatal care unit will be summaries at birth and at 4 weeks after birth, including the reasons for admissions. The Apgar score at 1, 5 and 10 minutes after birth will be summarised. Neonates will be grouped according to the Apgar score for each assessment time as: 0-3, 4-6, 7-10 and the corresponding frequencies tabulated. These data will be summarised by the treatment group and age stratum, and by treatment group and pregnancy type (singletons, twins), for the safety analysis set. Separate tables will be produced by country.

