### **Incidence of Serious Adverse Events**

All serious adverse events will be coded using MedDRA. In addition, congenital anomalies on the fetus/neonates will be coded using ICD-10 and these events will be classified as minor or major in accordance with the EMA guideline.

All serious adverse events will be listed.

Summary tables will be produced for the following:

- Maternal serious adverse events by SOC and PT
- Neonatal serious adverse events by SOC and PT
- Congenital anomalies on the fetus/neonates by ICD-10
- Congenital anomalies on the fetus/neonates classification as major by ICD-10
- Congenital anomalies on the fetus/neonates classification as minor by ICD-10

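### The post-trial serious-event rule names NICU twice and never NCU, so no admission-based criterion or duration explicitly covers the neonatal care unit

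*Protocol*

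**What the plan says.** Protocol section 8.4.1, under the heading on serious adverse events during post-trial follow-up, lists the occurrences to be recorded as serious. The line on neonatal admission reads: "Neonate admitted to the NICU regardless of duration or NICU for more than 2 hours". A sentence below the list says how to report such a case: "In case of admission to NICU or NICU, the reason for admission must be reported as a serious adverse event". NCU appears in neither place. The same list also contains death of the neonate, congenital anomaly, and "Medically important event".

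Elsewhere NICU and NCU are two units:

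- The protocol's abbreviation list has a separate entry for NCU, expanded as "neonatal care unit".
- Section 7.4.1 collects at birth "admission to neonatal intensive care unit (NICU) or neonatal care unit (NCU").
- The section 14.7 checklist asks the subject for "Admission to NICU/NCU (reason and duration"), both at delivery and 4 weeks later.
- SAP section 10.12, on neonatal health, states: "Admission to neonatal intensive care unit and/or neonatal care unit will be summaries at birth and at 4 weeks after birth".

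SAP section 10.12 also plans a table of "Neonatal serious adverse events by SOC and PT".

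**The concern.** A rule that gives one unit two different durations is probably not what its author meant. The unit left out is one that the trial defines and collects data on.

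The serious label carries obligations. Under section 8.4.2, a serious event goes to the sponsor's pharmacovigilance group within 24 hours of the investigator learning of it, with a completed form within 3 calendar days. Under section 8.5.3, a neonatal serious event not recovered at 4 weeks is followed to resolution, unless the condition is chronic or stable and stopping is agreed. The label also decides what enters the neonatal serious-event table. SAP section 10.1 has safety endpoints summarised by treatment group, with separate tables by country. Some of the planned 15-30 sites might supply the missing unit by inference and others might not. The counts would then partly reflect how each site read the rule.

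**Working it through.** The point depends on wording, and the plan states no figure to reproduce. The check is to read the rule literally and compare it with every other mention of the two units.

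**Step 1: the admission line.** It has two limbs joined by *or*.

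| Limb | Unit named | Duration |
|---|---|---|
| First | NICU | any |
| Second | NICU | more than 2 hours |

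Stays over 2 hours are a subset of stays of any length. The union of the limbs is every NICU stay, so the second limb adds nothing. A separate threshold would do some work only if it applied to a different unit.

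**Step 2: the reporting sentence.** It names NICU on both sides of its own *or*, so it does not supply the missing unit.

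**Step 3: the other mentions.**

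| Place | NICU named | NCU named | Content |
|---|---|---|---|
| Protocol, abbreviation list | yes | yes | separate entries |
| Protocol 7.4.1 | yes | yes | admissions collected at birth |
| Protocol 14.7 | yes | yes | reason and duration, at delivery and 4 weeks |
| SAP 10.12, neonatal health | yes | yes | admissions summarised, with reasons |
| Protocol 8.4.1, admission line | twice | no | serious-event criterion |
| Protocol 8.4.1, reporting sentence | twice | no | what to report |

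NCU is the only other neonatal unit that the protocol defines. The trial gathers what an NCU duration rule would need, but no such rule is written.

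**Step 4: whether another criterion fills the gap.**

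- Neonatal death and congenital anomaly apply whichever unit the neonate is in, but an NCU admission for any other reason falls outside them.
- The medically-important-event criterion also applies in any unit, but it rests on case-by-case judgement. Section 7.4.1 lets follow-up data come from the subject unless medical judgement is needed. An NCU stay reported on the checklist therefore becomes serious by this route only if someone then applies that judgement.
- The in-trial hospitalisation criterion in section 8.4.1 (at least 24 hours) stands under the heading for events during the trial and is worded for the trial subject. It does not clearly extend to a neonate after the trial.

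**Result.** An NCU admission can be recorded as serious, but no criterion makes it so on the fact or length of the admission.

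**The case against.** The strongest objection is that the text was read from PDF by a program and the suspected slip is a single letter. Both instances lie close together, so one reading error could have produced them both, and damage of that kind is not a fault in the plan. This cannot be excluded. It is made less likely because NCU was read correctly in the abbreviation list and, directly beside NICU, in sections 7.4.1 and 14.7. The repetition does not settle the matter either way, which is why the fix starts with the source text.

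The second objection is that little is lost. Admissions to both units are collected with reason and duration, and the SAP summarises both. A case missing from the serious-event table would still show in the neonatal health summary and could be reclassified. The serious-event form also carries instructions that are not in these documents, so variation between sites is a possibility and not something observed. All of this stands and limits the consequence. It does not restore the 24-hour report or the follow-up duty for a case that was not classed as serious at the time.

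A reader might also infer that the two NICU durations contradict each other, so that a site could apply a 2-hour limit to NICU stays. The documents do not support that. Because the limbs are joined by *or*, a shorter NICU stay already qualifies under the first, and the second is merely redundant.

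**Conclusion.** The defect is real but small. As worded, section 8.4.1 has a redundant second NICU limb and no explicit admission criterion or duration for NCU, a unit that the protocol and SAP otherwise treat as separate. Neonatal serious-event reporting, follow-up under section 8.5.3 and the SAP table may be incomplete or differ between sites.

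Two wider conclusions should be avoided. One is that NCU admissions have no serious-event rule at all, which fails because the other listed criteria can still capture them. The other is that every NCU stay over 2 hours is at stake. Some such cases would qualify under those other criteria, and a 2-hour NCU threshold exists only if the second NICU was meant to read NCU. That is the likeliest explanation, but the text does not say so.

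The number of affected cases cannot be estimated, because the documents give no NCU admission rate. Nothing here touches the primary endpoint, the sample size, the error rates or the in-trial serious-event definitions. The conclusion assumes that the text as read matches the sponsor's source document.

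**What to change.** 1. Check both sentences in section 8.4.1 against the source document. If the source names NCU, the point falls away. The SAP introduction lists two protocol documents, one for China and one for South Korea, Taiwan and Vietnam, so both should be checked.
2. If the wording is confirmed, reconcile both sentences with the abbreviation list, sections 7.4.1 and 14.7, and the neonatal health part of SAP section 10.12. Each unit should be named once, with the duration rule the sponsor intends. This point does not say which unit or duration rule is right.
3. Notify the sites, and check that the serious-event form instructions agree with the corrected text.
4. Check NICU and NCU admissions already collected, with their recorded reasons and durations, against the corrected wording before the neonatal serious-event table is produced.

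The cost is a short wording correction through the amendment process in section 12.1, a site notice and a check of data already being collected. No analysis method changes.
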